### **13.5 Analysis of Secondary Endpoints**

There is at least 74% probability of observing one or more rare (8% true probability) events, and 93% probability of observing toxicities that have a true occurrence of at least 15%. With 16 treated patients, the maximum width of a 90% two-sided exact binomial confidence interval for any estimated adverse event proportion will be no wider than  $\pm 22\%$ .

Progression-free survival will also be calculated. Progression-free survival, will be defined as the duration of time from start of treatment to time of progression or death, whichever occurs first and will be estimated using the Kaplan-Meier method. The disease control rate (Complete Response, Partial Response, and Stable Disease) at 24 weeks will also be calculated using the exact binomial distribution and 95% confidence interval.

We will explore the relationship between integrated biomarkers detected by cfDNA exome sequencing, WES, RNAseq expression profiling and response to Eribulin. We will use Fisher's Exact Test to assess the relationship between each biomarker and response to eribulin assuming a best overall objective response of 35%. Biomarkers may be continuous or binary. For example, with this design, assuming tissue is available on 100% of the sample, the probability of concluding eribulin response is related to the exploratory biomarker is 82%; given the unknown true response is 70% and 4% in positive marker versus negative marker patients, respectively, assuming 50% of the population is over-expressed for the biomarker or the biomarker is continuous and split at the median. The operating characteristics of this design are calculated using a two-sided exact test with 10% type I error.

We will explore the relationship between changes in the integrated biomarkers from baseline to cycle 3 due to eribulin treatment using a paired t-test. With 16 patients, we will have 81% power to detect an effect size of 0.67 using a paired t-test with a 0.1 two-sided significance level.

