### 1.4 Exploratory Objectives

- To determine any correlation between angiosarcoma or sarcoma subtype and response
- To determine any correlation between response and genomic characterization of the sarcoma
- To determine genomic and expression profile changes, via biopsy samples and/or circulating free DNA exome sequencing, over time after treatment with Eribulin

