## 9.2 Laboratory Correlative Studies

### 9.2.1 Peripheral blood cfDNA

- 9.2.1.1 Collection of Specimen(s): Two tubes of peripheral blood will be collected in Streck tubes (10 mL per tube) on each cycle day 1 prior to Eribulin infusion.
- 9.2.1.2 Shipping of Specimen(s): The samples will be immediately sent to the Broad Institute by courier at room temperature.
- 9.2.1.3 Site(s) Performing Correlative Study: Analysis of cfDNA by WES will be performed at the Broad Institute. Within three hours of collection, we will perform high-speed centrifugation to separate plasma and cells. We will extract cfDNA using magnetic bead-based protocols. To qualify the cfDNA obtained from each blood biopsy for WES, we will first assess the purity of tumor-derived cfDNA using ultra-low-pass whole genome sequencing (ULP-WGS).

The ULP-WGS is a low-cost approach to nominate samples containing sufficient fraction of tumor-derived DNA for WES. Briefly, cfDNA samples will be subjected to whole genome sequencing to an average of 0.1X genome-wide sequencing coverage. Samples with fewer than 150,000 reads (0.005X) will be excluded due to insufficient coverage for analysis. We will utilize the statistical approach from the HMMcopy software(28) to correct for GC-content and mappability (sequence uniqueness) biases in read counts within genomic bins of 1Mb, which substantially improves signal to noise ratio. Next, we will use a modified approach from the TITAN(29) framework to perform segmentation, copy number prediction, and purity and ploidy estimation. This approach is optimized for increased sensitivity to detect events from low purity tumor-derived DNA in the absence of a control sample. Benchmarking of the purity estimates has been carried out using simulation of tumor-normal mixing and comparison to corresponding WES data, revealing a robust lower estimation level of 5% purity. As described in our Preliminary Data, we expect at least 50% of blood biopsies to have sufficient tumor-derived cfDNA to proceed with WES.

In those samples deemed by ULP-WGS to be adequate for WES, the exome will be selected using solution-phase hybrid capture and sequencing will be performed using the Illumina HiSeq2500, as described above. WES data will be analyzed for base substitutions, small insertions/deletions, and copy number alterations(30-34).

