- E- Urine or serum beta-HCG Must be repeated if not performed within 72 hours of cycle 1 day 1
- F- Biopsy 1 will occur after registration and prior to C1D1. Biopsy 2 will occur prior to the first imaging and C3D1. Platelet count and PT/PTT required pre biopsy 2 or per institutional standards. When possible the biopsy should be multiple cores or excisional. If the biopsy is considered unsafe the requirement may be waived after discussion with the overall PI.
- G- cfDNA will be collected after registration (prior to C1D1) and every D1 thereafter
- H- See section 5.8 for AE and SAE follow-up.
- I- ECG monitoring only required for screening, C2D1 and C3D1 unless the criteria for continued monitoring are met as per section 6.3. ECG does not need to be repeated on C1D1 if obtained within 15 days of C1D1, unless clinically indicated.

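### For cfDNA, the baseline-to-cycle-3 paired t-test drops patients who progress at the first scan, and its 81% power assumes 16 complete pairs

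*Combined protocol and SAP*

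**What the plan says.** Section 1.4 sets an exploratory objective on genomic and expression changes, "via biopsy samples and/or circulating free DNA exome sequencing, over time after treatment with Eribulin".

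Section 9.2.1 provides that "Two tubes of peripheral blood will be collected in Streck tubes (10 mL per tube) on each cycle day 1 prior to Eribulin infusion". Footnote G of the study calendar agrees: "cfDNA will be collected after registration (prior to C1D1) and every D1 thereafter". The calendar marks no off-study cfDNA draw. Each blood sample is screened by low-pass sequencing and goes to exome sequencing if adequate. Section 9.2.1 expects at least half of samples to pass.

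Section 13.5 names one analysis of change. It looks at "changes in the integrated biomarkers from baseline to cycle 3 due to eribulin treatment using a paired t-test" and adds: "With 16 patients, we will have 81% power to detect an effect size of 0.67", "using a paired t-test with a 0.1 two-sided significance level". It gives no rule for a missing cycle 3 sample and no allowance for lost pairs. The Fisher example in the same section is likewise worked out "assuming tissue is available on 100% of the sample".

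Three other provisions decide who has a cycle 3 sample. Section 11.1 and the calendar put the first scan before C3, with a window of one week either way (footnote D). Section 5.7 lists disease progression as a reason to end protocol therapy. Section 9.2.2 and calendar footnote F put Biopsy 2 before the first imaging and before C3D1.

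**The concern.** The later of the two time points in the test comes just after the event that removes patients. Someone stopped for progression at the first scan has given blood before C1D1 and on C2D1, and in the usual sequence gives none on C3D1. The test as written cannot use that patient, although a post-treatment sample exists.

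The loss is not random. The patients removed are the early progressors, while sections 2.4 and 9.1 say that the sequencing is meant to find indicators of resistance as well as of response. A mean change among those with a cycle 3 draw describes patients controlled at about week 6. It describes the treated population only if their change resembles that of the patients who left.

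The stated power also rests on 16 pairs, which early exits make unlikely for cfDNA.

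**Working it through.** **1. The plan's own figure.** Inputs from section 13.5: n = 16, effect size d = 0.67, two-sided alpha 0.10. Power of a paired t-test is P(T > t crit), where T is noncentral t with n − 1 degrees of freedom and noncentrality d√n. The opposite tail is negligible.

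- t crit (15 df, upper 5%) = 1.753; noncentrality = 0.67 × √16 = 2.68.
- Power = 81.9%, which agrees with the stated 81%.

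**2. Which samples exist if progression is found at the first scan before C3D1.**

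| Sample | Scheduled | Available |
|---|---|---|
| cfDNA, baseline | before C1D1 | yes |
| cfDNA, C2D1 | about week 3 | yes |
| cfDNA, C3D1 | after the first scan | normally no |
| Biopsies 1 and 2 | before C1D1; before the first scan | yes |

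The cfDNA pair is lost and the tissue pair is kept.

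**3. How many cfDNA pairs might remain.** The documents give no week-6 rate for this population. Assumption: the eribulin soft-tissue sarcoma trial in section 2.2.3 is a guide, with constant hazard. Its strata are other sarcoma types, so this gives a range and not a prediction. Deaths count as events.

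- *From median PFS m (months):* S(6 wk) = 0.5^(1.38/m), with 6/4.345 = 1.38 months.
  - m = 2.1: S = 0.634, 36.6% with an event, 16 × 0.634 = 10.1 pairs.
  - m = 2.9: S = 0.719, 28.1% with an event, 16 × 0.719 = 11.5 pairs.
- *From the 12-week progression-free rate p:* S(6 wk) = √p.
  - p = 24%: S = 0.490, 51.0% with an event, 16 × 0.490 = 7.8 pairs.
  - p = 46.9%: S = 0.685, 31.5% with an event, 16 × 0.685 = 11.0 pairs.

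Together, 28% to 51% would have an event by week 6, leaving about 8 to 11 pairs.

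**4. Power at d = 0.67 with fewer pairs** (formula of step 1).

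| Pairs | Power | Effect size for 80% power |
|---|---|---|
| 16 | 81.9% | 0.65 |
| 12 | 70.2% | 0.77 |
| 11 | 66.4% | 0.81 |
| 10 | 62.2% | 0.85 |
| 9 | 57.6% | 0.91 |
| 8 | 52.6% | 0.98 |

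At 8 to 11 pairs, power is 53% to 66%. The most favourable input in step 3 (11.5) lies between 11 and 12 pairs, and 12 would give 70%.

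**5. Inadequate cfDNA.** If only half of the patients had an adequate pair, 8 of 16 would remain with no early exits at all (53%). This loss comes on top of step 3 and would thin any model, not only the paired test.

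**6. Would extra draws raise power?** Assume equal correlation between draws and contrast baseline with the mean of C2D1 and C3D1, with all 16 patients complete. The SD of the contrast shrinks from √(2(1−ρ)) to √(1.5(1−ρ)), a factor free of ρ. Let the C2 shift be a fraction f of the C3 shift. Then d = 0.67 × √(2/1.5) × (1 + f)/2.

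| f | d | Power, n = 16 |
|---|---|---|
| 1.00 | 0.774 | 90.4% |
| 0.75 | 0.677 | 82.6% |
| 0.50 | 0.580 | 71.5% |

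The planned test has 81.9%. The averaged contrast can be better, equal or worse, depending on a time course that the documents do not give.

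**The case against.** The best defence is that this is one exploratory comparison in a 16-patient pilot, and that early progressors are not lost to the study. Their paired biopsies survive, and section 1.4 allows biopsies and/or cfDNA. That stands: the point is confined to cfDNA.

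A reader might infer more than the documents support:

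- *That the objective on change over time goes unanalysed.* Baseline to cycle 3 is a change over time, and section 9.2.2 also plans pre- against post-treatment comparisons of tissue.
- *That the other draws are unused or money wasted.* The Fisher analysis covers cfDNA markers and names no time point, so later draws are not excluded there. The documents give no costs. What is missing is a prespecified change analysis.
- *That modelling more draws buys power.* Step 6 shows that this needs a nearly full effect by C2. With complete data, the C3D1 change from an unstructured model is essentially the paired comparison.
- *That nobody who progresses at the first scan can have a C3D1 draw.* The one-week window lets some scans follow C3D1, hence normally rather than always.
- *That the paired t-test is invalid because "Biomarkers may be continuous or binary".* That sentence belongs to the Fisher paragraph. For binary differences at nominal 10%, the test's actual size is about 4% to 10% across discordance of 10% to 50%, so this is minor and not pressed.

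The benchmark is also fairly called unstable. A 2.1-month median with constant hazard implies 40% progression-free at 12 weeks, against 24% reported for that stratum (95% CI 9.8 to 41.7). This is why both routes are shown as a range.

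**Conclusion.** The point holds for cfDNA, as a low-cost improvement and not as a flaw in the trial's main conclusions. As written, the test selects patients still on treatment at cycle 3, although early progressors normally have a usable C2D1 draw. The 81% is arithmetically right but needs 16 complete pairs. About 8 to 11 pairs and 53% to 66% power are more plausible before assay failure, if the sarcoma benchmarks carry over with constant hazard.

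The selection follows from the schedule alone. Its direction and size for any given marker cannot be derived from the documents. Tissue biomarkers are not affected by exit at the first scan, though patients who leave before Biopsy 2 lose that pair too. The primary response endpoint and its decision rule are untouched.

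**What to change.** In section 13.5:

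1. For continuous cfDNA markers, replace the paired t-test with a likelihood-based repeated-measures model using baseline, C2D1, C3D1 and, if numbers allow, later Day 1 draws. Report the C2D1 and C3D1 changes from baseline, with the number of patients contributing at each.
2. State that the 81% holds only for 16 complete pairs, and give power for a plausible smaller number, for example 8 to 11.
3. Keep the paired test for the biopsy data.
4. Claim less selection and retention of early progressors as the benefit, not a general gain in power.

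The cost is some plan wording and modest extra analysis. No new visits or draws are needed, since the protocol already collects the samples and screens them for sequencing. The downside is that the model assumes dropout depends on observed data. Exit is driven by progression, which the model does not contain, so the assumption should be stated with the result. It is still weaker than what the complete-pair test needs, namely that patients with a C3D1 sample represent everyone treated. A patient with no post-baseline draw contributes no observed change under either method. The choice should be written down before data are seen, because picking time points afterwards in 16 patients invites selective reporting.

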### **13.6 Reporting and Exclusions**

### 13.6.1 Evaluation of Toxicity

All participants will be evaluable for toxicity from the time of their first treatment. All patients who receive at least one dose of Eribulin will be included in the toxicity analysis. This includes participants who receive study drug and are ultimately deemed ineligible.

### 13.6.2 Evaluation of the Primary Efficacy Endpoint

All participants who received at least one dose of Eribulin will be included in the overall response rate analysis. All eligible participants included in the study must be assessed for response to treatment, even if the patient is ineligible or there are major protocol therapy deviations, following intent-to-treat.

## 14. PUBLICATION PLAN

The results should be made public within 24 months of reaching the end of the study. The end of the study is the time point at which the last data items are to be reported, or after the outcome data are sufficiently mature for analysis, as defined in the section on Sample Size, Accrual Rate and Study Duration. If a report is planned to be published in a peer-reviewed journal, then that initial release may be an abstract that meets the requirements of the International Committee of Medical Journal Editors. A full report of the outcomes should be made public no later than three (3) years after the end of the study.

**15. APPENDIX A PERFORMANCE STATUS CRITERIA**

ECOG Performance Status Scale		Karnofsky Performance Scale	
Grade	Descriptions	Percent	Description
0	Normal activity. Fully active, able to carry on all pre-disease performance without restriction.	100	Normal, no complaints, no evidence of disease.
		90	Able to carry on normal activity; minor signs or symptoms of disease.
1	Symptoms, but ambulatory. Restricted in physically strenuous activity, but ambulatory and able to carry out work of a light or sedentary nature (e.g., light housework, office work).	80	Normal activity with effort; some signs or symptoms of disease.
		70	Cares for self, unable to carry on normal activity or to do active work.
2	In bed <50% of the time. Ambulatory and capable of all self-care, but unable to carry out any work activities. Up and about more than 50% of waking hours.	60	Requires occasional assistance, but is able to care for most of his/her needs.
		50	Requires considerable assistance and frequent medical care.
3	In bed >50% of the time. Capable of only limited self-care, confined to bed or chair more than 50% of waking hours.	40	Disabled, requires special care and assistance.
		30	Severely disabled, hospitalization indicated. Death not imminent.
4	100% bedridden. Completely disabled. Cannot carry on any self-care. Totally confined to bed or chair.	20	Very sick, hospitalization indicated. Death not imminent.
		10	Moribund, fatal processes progressing rapidly.
5	Dead.	0	Dead.

